5.1.2. Arm 2 – Temozolomide plus isotretinoin

This arm was originally designed to assess the MTD of carboplatin (CBT) in combination with fixed doses of isotretinoin (cRA). The accrual to this arm of the trial was also completed and the MTD for this combination was established with carboplatin (AUC 5 on day 1) and isotretinoin (100 mg/m2/day on days 1-21). However, in the current proposal, we will not use carboplatin and will replace this with temozolomide. Thus, the combination of interest in Arm 2 will be dose-dense temozolomide with isotretinoin. A recent phase I trial of temozolomide in combination with several different agents has established the MTD of temozolomide adminstered in combination with isotretinoin at 150 mg/m2/day of temozolomide on days 1-7 and days 15-21 in patients with glioblastoma (Gilbert et al, Neuro-oncology 2010). Thus, we propose to use this regimen in the phase II portion of the current trial without the need for a phase I component.

5.1.3. Arm 3 – Vorinostat plus isotretinoin plus temozolomide

This arm will assess the MTD of vorinostat and temozolomide in combination with fixed doses of cRA. The enrollment will proceed as outlined for Arm 1 and 2 (cohorts of 3 patients enrolled to each dose level), declaring MTD for vorinostat in combination with temozolomide and cRA once DLT is noted. In this arm, cRA will be given on days 1-21 and vorinostat on days 1-7 and 15-21. Temozolomide will be administered orally on days 1-7 and 15-21. Days 22-28 will be considered a notreatment "rest" period. A maximum of three dose levels of vorinostat will be used as shown in the table below.

Level	Arm 3		
	Vorinostat	cRA	Temozolomide
	(mg/day x days 1-7 &	(mg/m2/day x 21	(mg/m2/day on
	15-21)	days)	days 1-7 & 15-21

-111	300	100	100
-11	300	100	125
-1	400	100	125
0 (starting dose)	400	100	150
I	500	100	150

5.1.3.1 Escalation of Dose Level

- If the initial cohort of patients at starting dose level 0 do not experience DLT, the next cohort of patients will be treated by dose escalation to level I (with increase in the dose of vorinostat). If no patients experience DLT in this cohort, 3 more patients will be enrolled to expand this cohort to a total of 6 patient to confirm that MTD has been achieved. If no DLT is noted or if only 1/6 patients experience DLT after this expansion of level I, this dose level will be declared the MTD and hence the phase II dose.
- If 2/6 patients have DLT after expansion of dose level I, dose level 0 will be declared as the MTD and hence the phase II dose.

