5.1.3.2 De-escalation of Dose Level

If Dose level 0 exceeds the MTD, lower doses will be studied as noted in the table above. If 1/3 patients have DLT at any dose level, the cohort will be expanded by 3 more patients. If ≥2/6 patients experience DLT, the MTD will be considered as being exceeded and the dose will be de-escalated to the next lower dose level and 3 new patients will be enrolled at that level. If none or only 1/6 patients experience DLT after dose de-escalation to the lower level, this dose level will be declared as the MTD, and will be utilized for the phase II component of the study.

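### Arm 3, phase I: 2/6 DLTs at level I has two written consequences, one of which can declare level 0 the MTD on 0/3

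*Combined protocol and SAP*

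**What the plan says.** Section 5.1.3 runs Arm 3 in "cohorts of 3 patients enrolled to each dose level". In Section 5.1.3.1 the condition for moving up is "If the initial cohort of patients at starting dose level 0 do not experience DLT"; the next cohort then goes to level I. If that cohort is also free of DLT, "3 more patients will be enrolled to expand this cohort to a total of 6 patient to confirm that MTD has been achieved". Level I becomes the MTD with 0 or 1 DLT in six. Otherwise the rule, less its last word, is: "If 2/6 patients have DLT after expansion of dose level I, dose level 0 will be declared as the MTD and hence the phase II". No further patients are called for at level 0. The section does not say what follows more than two DLTs in six at level I.

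Section 5.1.3.2, on de-escalation, opens with the case in which level 0 exceeds the MTD. It then states a general expansion rule: "If 1/3 patients have DLT at any dose level, the cohort will be expanded by 3 more patients". For two or more DLTs in six, "the dose will be de-escalated to the next lower dose level and 3 new patients will be enrolled at that level", and the lower level becomes the MTD with no more than one DLT in six.

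Section 11.1.3 repeats both sets of rules. Section 5.2.1 takes the phase II dosage from the phase I MTD.

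**The concern.** A result of 2/6 at level I falls under both sections. One closes dose finding at once. The other asks for three more patients at level 0 first. Whoever makes the decision must choose between two written instructions at the moment that fixes the Arm 3 dose.

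The choice decides whether the MTD rests on three patients or six. On this path level 0 lies one vorinostat step below a level with 2/6 DLTs. Section 2.6 notes that dose-dense temozolomide had not yet been explored with vorinostat, so there is little outside evidence to lean on. Arm 3 is not small: in the plan's simulations it averages 43.5 to 43.8 patients when all three medians are 3 months.

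**Working it through.** The plan gives no error rate or target DLT rate for this rule, so there is no figure to reproduce. The true DLT rates below are assumptions, shown as a range, with patients taken as independent.

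**Do both rules reach 2/6 at level I?** Section 5.1.3.1 describes expansion of level I only after 0/3. Expansion after 1/3 at level I appears only in Section 5.1.3.2. With DLT rate p and q = 1 − p at level I, there are two routes to exactly 2/6:

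- 0/3 then 2/3: q³ × 3p²q = 3p²q⁴
- 1/3 then 1/3: (3pq²)² = 9p²q⁴

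Whatever p is, 9/(9 + 3) = 75% of the 2/6 results come by the second route. That route depends on Section 5.1.3.2 for its expansion, and the sentence after the expansion rule there prescribes de-escalation with new patients.

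**What 0/3 shows about level 0.** The one-sided 95% upper limit for the DLT rate after 0/3 is 1 − 0.05^(1/3) = 63.2%. With six patients it is 39.3% (0/6) or 58.2% (1/6), by the exact binomial method.

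**Chance that level 0 passes.** Section 5.1.3.2 is read here as pooling the three earlier and three new level 0 patients.

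- Immediate declaration: A = (1−p)³
- At most one DLT in three new patients: c = (1−p)³ + 3p(1−p)²
- With the new patients: A × c. Overturned after 0/3: 1 − c

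| True level 0 rate | A | A × c | 1 − c |
|---|---|---|---|
| 20% | 51.2% | 45.9% | 10.4% |
| 25% | 42.2% | 35.6% | 15.6% |
| 1/3 | 29.6% | 21.9% | 25.9% |
| 40% | 21.6% | 14.0% | 35.2% |
| 50% | 12.5% | 6.25% | 50.0% |

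**How often the rules diverge.** Divergence needs 0/3 at level 0 and then 2/6 at level I. With p₀ and p₁ the rates at the two levels and q₁ = 1 − p₁, the path probability is (1−p₀)³ × 12p₁²q₁⁴. Multiplying by 1 − c at p₀ gives the chance that the dose differs.

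| Level 0 / level I rate | Path | Different dose |
|---|---|---|
| 20% / 33% | 0.512 × 0.2633 = 13.5% | × 0.104 = 1.4% |
| 33% / 40% | 0.3008 × 0.2488 = 7.5% | × 0.255 = 1.9% |
| 40% / 50% | 0.216 × 0.1875 = 4.1% | × 0.352 = 1.4% |
| 50% / 50% | 0.125 × 0.1875 = 2.3% | × 0.500 = 1.2% |

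These count exactly 2/6, the case that Section 5.1.3.1 names.

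**The case against.** The strongest defence is scope. Section 5.1.3.1 has a specific rule for level I. Section 5.1.3.2 is about de-escalation and begins with level 0 exceeding the MTD, so its call for new patients could be meant only for untested lower levels. Arm 1 (Section 5.1.1) likewise declares the previous level with no stated top-up. This reading is possible, and immediate declaration may be what was intended. It is weak as a reading of the text, because the expansion rule is expressly not limited to lower levels and is needed for 1/3 at level I. Even if it is accepted, level 0 can still become the MTD on 0/3, since that follows from Section 5.1.3.1 alone.

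A reader might infer that the plan already requires six patients for every MTD. The documents do not support that. Section 5.1.3.2 does not say what follows 0/3 at a lower level, and only level I has an unambiguous expansion after 0/3.

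A reader might also take the relative reduction in false acceptance, 26% to 50% for true rates of 1/3 to 50%, as the effect on the trial. It leaves out the triggering event at level I, so the absolute effect is far smaller.

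Nor can level 0 be assumed to enter phase II unchanged. Sections 9.1 and 11.2 require a toxicity check after every 10 patients per arm, with a lower starting dose or closure to accrual. Section 5.4.2 gives dose reductions, and Section 5.4.2.3 starts temozolomide at 125 mg/m², which does not match the 150 mg/m² of level 0 and itself needs reconciling. These safeguards limit the harm, but they act only once phase II patients are exposed.

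Finally, the intolerance of the carboplatin triplet (Section 2.11) is put down mainly to carboplatin–vorinostat overlap, so it says little about this regimen. Any effect on the PFS comparison is unquantified.

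**Conclusion.** The point holds as an unreconciled decision rule: 2/6 at level I of Arm 3 meets two different instructions, repeated in the statistical section, and results above 2/6 are not covered by Section 5.1.3.1. Under one instruction the MTD can rest on 0/3.

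The expected numerical effect is small: the path arises in about 2% to 13.5% of trials, and the dose differs in about 1% to 2%. These figures rest on assumed DLT rates, independence, pooling of the old and new level 0 patients, and exactly 2/6. The reason to act is that the ambiguity sits at the decision that sets the Arm 3 phase II dose, bears on patient safety, and is cheap to remove. The documents do not show that either rule is the wrong one.

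**What to change.** Reconcile Sections 5.1.3.1, 5.1.3.2 and 11.1.3 so that two or more DLTs in six at level I leads to one stated action, including results above 2/6. State how many patients the declared MTD then rests on. Which rule to keep is for the sponsor and investigators to decide.

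The cost is protocol wording. If the sponsor keeps the Section 5.1.3.2 version, it adds at most three phase I patients, and only on this path.

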5.1.3.2 De-escalation of Dose Level

If Dose level 0 exceeds the MTD, lower doses will be studied as noted in the table above. If 1/3 patients have DLT at any dose level, the cohort will be expanded by 3 more patients. If ≥2/6 patients experience DLT, the MTD will be considered as being exceeded and the dose will be de-escalated to the next lower dose level and 3 new patients will be enrolled at that level. If none or only 1/6 patients experience DLT after dose de-escalation to the lower level, this dose level will be declared as the MTD, and will be utilized for the phase II component of the study.

5.2. Phase II Component

5.2.1. Non-surgical Arm

In this component, patients will be randomized between three competing treatment arms: vorinostat + cRA, versus TMZ + cRA, versus vorinostat + cRA + TMZ using an adaptive randomization design (see 11.0 Statistical Section). The dosage of agents in each arm will be derived from the MTD of the combination determined in the phase I component of the study. The treatment schedule will be identical to that described above in the phase I component, with each course comprising 28 days (+ 3 days). Patients will continue treatment for at least one year from registration provided they experience neither tumor progression nor unacceptable toxicity (see 8.9). Treatment beyond this period is at the discretion of the treating physician after discussion with the patient. Vorinostat will continue to be provided free of charge to patients continuing treatment beyond 1 year.

Optional procedures: if available, brain tumor tissue from prior surgical procedures (original surgery, or definitive surgery, or the surgery closest to initiation of this clinical trial) will be obtained for determination of acetylation status and p21 levels (see 6.7). Blood samples for acetylation status of histones and p21 levels in

peripheral mononuclear cells will be also collected at baseline prior to treatment (6.6). Patients enrolled in arms 1 (vorinostat + cRA) and 3 (vorinostat + cRA + TMZ) will be evaluated with blood samples before and after treatment with vorinostat in day 1 of cycles 1 and 2 (see 7.10).

5.2.2. Surgical Arm

Ten patients who require resection for recurrent glioblastoma multiforme will be included in this arm of the study. These patients will receive treatment with vorinostat at a dose of 400 mg once daily for 3 consecutive days prior to surgery. Blood samples for acetylation status of histones and p21 levels in peripheral mononuclear cells will be collected at baseline prior to treatment, and after the first dose of vorinostat. The last dose prior to surgery will be administered the morning of surgery within 6 hours of the tumor removal. Tumor tissue and intraoperative blood samples will be obtained for analysis of drug levels, histone acetylation and p21 levels. Approximately 2 weeks after surgery is performed, each patient will be randomized to one of the three treatment arms of the phase II component (arm 1: vorinostat + cRA; arm 2: TMZ + cRA; arm 3: vorinostat + cRA + TMZ). Patients enrolled in arms 1 and 3 will be evaluated with blood samples before and after treatment with vorinostat in cycles 1 and 2 as described for patients in the non-surgical arm (see 5.2.1, and 7.10). In surgical patients, cycle 1 will be the first cycle of treatment after surgery.

Progression Free Survival (PFS) in patients enrolled in the surgical arm will be determined from the date of randomization into the chemotherapy arms (i.e. after surgery for resection of recurrent tumor), and not from the date of registration in the trial.

5.3. Definition of dose limiting toxicities (DLT)

Toxicities will be graded according to the Common Terminology Criteria for Adverse events (CTCAE) Version 3.0. (see Appendix B). If multiple toxicities are seen, the presence of DLT should be based on the most severe toxicity experienced. DLT will be defined as any of the following events occurring during treatment and attributable to the study drugs:

5.3.1 Any grade 4 hematological toxicity excluding lymphopenia . (if the toxicity is Grade 4 neutropenia without fever, it must NOT resolve/regress to \leq Grade 1 within 7 days of onset to be considered a DLT).

5.3.2 Any non-hematologic grade 3 toxicity, weight gain (in patients on steroids), alopecia, and venous thromboembolic disease *. Grade 3 nausea, vomiting, or diarrhea that cannot be controlled by medical therapy will be considered dose-limiting. Isolated laboratory abnormalities not of clinical significance will be discussed with the IRB and the decision to declare these DLTs will be based on the IRB recommendations.

5.3.3 Failure to recover from toxicities to be eligible for re-treatment within 4 weeks of the last dose of the drugs.

*Non-Relevant Toxicities for Brain Tumor Protocols

Lymphopenia is a common finding among patients with primary brain tumors and is directly attributable to concurrent use of corticosteroids. To date, even Grade III lymphopenia has not been associated with a worsening of clinical outcome. Therefore, we will not consider this parameter in the determination of optimal dosing of drugs.

Weight gain is a common finding among patients with primary brain tumors. This too is directly attributed to the concurrent use of corticosteroids. Doses of steroids or study agents will not be modified as a consequence of weight gain. Corticosteroid dosage will be based on maintenance of control of edema in the brain and the standard clinical practice to use the minimal effective dose of corticosteroids will be employed.

Alopecia is a common occurrence in patients with brain tumors as a consequence of cranial radiotherapy. Alopecia will not be recorded or graded as toxicity.

Venous thromboembolic disease is a common complication occurring in up to 30% of patients with malignant gliomas [32, 33]. In this study, patients who develop deep vein thrombosis may receive anticoagulation and resume therapy once they are stable on anticoagulation. Grade III deep vein thrombosis will not be considered a DLT.

5.4. Dose modifications

5.4.1 Subsequent Cycles

Treatment cycles will be repeated every 28 days (+ 2 days) from day 1 provided that the tumor has not progressed and the patient has recovered from treatment-related adverse events associated with a prior course. Recovery has occurred once all of the following conditions have been met:

a) ANC >1500/mL;

b) Platelet Count >100,000/mL;

c) All drug-associated non-hematological toxicities have recovered to either Grade 0 or 1(except for deep venous thrombosis as below).

If recovery has not occurred by **Day 28** (+ 3 days), the subsequent cycle will be delayed until these criteria have been met. If the patient has not recovered within 4 weeks of rest, he/she will be taken off study. However, if the patient develops a lower extremity deep venous thrombosis and requires anticoagulation or intervention (grade 3 toxicity), treatment may be restarted after a 2 week rest period if the patient

is stably anticoagulated and is judged medically stable to begin chemotherapy, in the opinion of the treating physician. (Please note: DVT is graded in the CTC version 3.0 as grade 1= not defined, grade 2= DVT without need for anticoagulation or intervention, grade 3= DVT needing anticoagulation or intervention).

The administration of vorinostat, isotretinoin and temozolomide in subsequent cycles will continue at the same doses without interruption as long as there is no tumor recurrence or progression and toxicity is acceptable.

5.4.2 Dosage Reduction

Patients experiencing toxicity will be dose reduced according to the agent causing the toxicity. Because of the different profile of side effects of agents combined in Arms 1 and 2 (vorinostat + cRA; TMZ + cRA), no significant overlapping toxicities are expected. In case of thrombocytopenia or anemia in Arm 3 (vorinostat + cRA + TMZ), temozolomide will be dose-reduced first, and then vorinostat on an alternating basis for each time a dose reduction becomes necessary.

5.4.2.1 Vorinostat

Vorinostat will be administered from day 1 -14 in arm 1 and on days 1-7 and 15-21 in arm 3. Treatment will be initiated at the MTD dose determined in the phase I component of the trial for each arm. This dose will be maintained as long as there are no toxicities \geq grade 3. For grade 3 or greater toxicities, treatment will be withheld and the patients will be monitored until toxicities resolve to < grade 2 (except for deep venous thrombosis as noted in section 5.3). Subsequent treatment will be at one dose level lower than the one that caused the toxicity. If there is grade 3 or greater non-hematologic toxicity, a minimum of 2-week rest period will be required. Subsequently, patients will restart treatment at one dose level less than the one that resulted in the toxicity as indicated below.

Dose adjustments for the subsequent cycles: dose will be one level below the dose that produced toxicity of grade 3 or greater per dose schedule changes indicated below. If grade 3 or 4 toxicity recurs, patients will again discontinue the vorinostat until toxicity returns to grade 1 or less. The estimated dose levels below are shown for various MTD that may be determined in the phase I study.

In case of thrombocytopenia or anemia in Arm 3 (vorinostat + cRA + TMZ), TMZ will be dose-reduced first, and then vorinostat on an alternating basis for each time a dose reduction becomes necessary.

Dose Level:	-2	-1	0
Drug			MTD Phase I
Vorinostat	N/A	200 mg once daily	300 mg once daily
	200 mg once daily	300 mg once daily	400 mg once daily

300 mg once daily	400 mg once daily	500 mg once daily

Only 2 dose reductions of vorinostat are permitted as above. If the patient experiences grade 3 or greater toxicity after 2 dose reductions, he/she will be taken off study. If starting dose is 300 mg once daily, only 1 dose reduction of vorinostat is allowed.

5.4.2.2 Isotretinoin

Isotretinoin will be administered from day 1 to day 21 in the 3 arms of the study at an initial dose of 100 mg/m2/day. Doses will be rounded down, depending on body surface area and available capsule sizes. Treatment will continue at the same dose as long as there are no toxicities \geq grade 3. For grade 3 or greater toxicities, treatment will be withheld and the patients will be monitored until toxicities resolve to < grade 2 (except for deep venous thrombosis as noted in Section 5.3).

Dose adjustments for the subsequent cycles: Subsequent cycles will start (as long as the treatment is beneficial) after resolution of toxicities to grade 1 or less (except for deep venous thrombosis as noted in Section 5.3). A minimum of 2-week rest period will be required if there is grade 3 or greater non-hematologic toxicity.

Dosage of cRA for the subsequent cycle will be one dose level below the dose that produced toxicity of grade 3 or greater as shown below.

Dose level:	-2	-1	0
Isotretinoin	50 mg/m²	75 mg/m²	100mg/m ²

Only 2 dose reductions of cRA are permitted. If the patient experiences grade 3 or greater toxicity after two dose reductions, he/she will be taken off study.

5.4.2.3 Temozolomide

Dosing is based on adverse events (AEs) during the prior treatment cycle. If multiple AEs are seen, the dose administered should be based on the dose reduction required for the most severe grade of any single AE.

Dose Level	Dose mg/m ²	Remarks
- 2	75	Reduction if prior AE
-1	100	Reduction if prior AE
		Starting dose for cycle 1; increase to 150 mg/m^2 for cycle 2 and beyond if
0	125	non hematologic toxicity \leq grade 2

		and hematologic toxicity \leq grade 1
+1	150	Highest possible dose level

a) First Cycle: Temozolomide will be initiated at a dose of 125 mg/m²/day.

- b) Second Cycle: The dose of temozolomide will be determined according to: (1) treatment related non-hematologic AE during the preceding treatment cycle, as well as (2) the worst ANC and platelet counts. For patients at dose level 0, the dose may be increased to 150 mg/m2/dose for cycle 2 and beyond. If this dose is not tolerated, the dose may be reduced to the previous dose level.
- c) Delay: On day 1 of each cycle (within the prior 72 hours), ANC $\ge 1.5 \times 10^{9}$ /L, platelet count $\ge 100 \times 10^{9}$ /L and all grade 2, 3 or 4 nonhematologic AEs (except for alopecia, nausea, vomiting, weight change or DVT/PE – see section 5.3.3 – nonrelevant toxicities) must have resolved (to grade ≤ 1). For DVT/PE, the patient must have had adequate management of the event and be medically stable as determined by the treating physician prior to resuming treatment – this will be considered on a case by case basis after discussion between the treating physician and the study chair.

If AEs persists, treatment should be delayed by 1 week for up to 4 consecutive weeks. If, after 4 weeks of delay, all treatment related AEs have still not resolved (to grade \leq 1): then any further treatment with temozolomide should be stopped.

Dose Escalations and Reductions: If, during the first cycle, all hematologic AEs observed were \leq grade 1 and treatment related non-hematologic AEs observed were grade \leq 2 (except alopecia, lymphopenia, nausea, vomiting, weight gain and DVT/PE) then the temozolomide dose can be raised to 150 mg/m2/dose for subsequent cycles.

Dose reductions: If any treatment related non-hematologic AE observed was grade > 2 (except alopecia, lymphopenia, nausea, vomiting, weight gain and DVT/PE) and/or if platelets < 50×10^{9} /L and/or ANC < 1×10^{9} /L, then the dose should be reduced by one dose level. Patients who require more than three dose reductions will have treatment stopped.

If any treatment-related non-hematologic AE observed was grade 4 (except alopecia, lymphopenia, nausea, vomiting, weight gain and DVT/PE) then temozolomide treatment should be stopped.

Subsequent cycles: Any dose reductions of temozolomide will be determined according to: (1) non-hematologic AE during the preceding

treatment cycle, as well as (2) the lowest ANC and platelets observed. No dose escalation should be attempted. The same dose reductions as for the second cycle should be applied. Important: If the dose was reduced or delayed for AEs, there will be no dose re-escalation in subsequent treatment cycles.

Summary of Dose Modifications or Discontinuation for Temozolomide-Related Adverse Events

Worst Treatment-Related Non-Hematologic AE (except for alopecia, nausea, and vomiting) During the Previous Cycles			
Grade	Dose Modification		
0-2	No dose modifications for non-hematologic AEs. Dose reductions based on ANC and platelet counts are applicable.		
3	Reduce by one dose level (except alopecia, lymphopenia, nausea, vomiting, weight gain and DVT/PE).		
4	Stop (except alopecia, lymphopenia, nausea, vomiting, weight gain and DVT/PE). Dose modifications based on ANC and platelet counts are not applicable.		

Worst Treatment-Related Hematologic AE During the Previous Cycle

Worst A	ΑE	Platelets		
		≥100 x 10 ⁹ /L	50 – 99 x 10 ⁹ /L	< 50 x 10 ⁹ /L
	≥ 1.5 x 10 ⁹ /L	Dose unchanged	Dose unchanged	Reduce by 1 dose level
ANC	≥1 & <1.5 x 10 ⁹ /L	Dose unchanged	Dose unchanged	Reduce by 1 dose level
	< 1 x 10 ⁹ /L	Reduce by 1 dose level	Reduce by 1 dose level	Reduce by 1 dose level

Note: A complete blood count must be performed on days 14 and 28 (\pm 72 hours) after the first daily dose of each treatment cycle.

Hematologic AE on Day 1 of Each Cycle (within the prior 72 hours before Day 1)			
AE	Delay		
ANC< 1.5 x 10 ⁹ /L and/or Platelet count < 100 x 10 ⁹ /L	Delay up to 4 weeks until all resolved. If unresolved after 4 weeks then stop. If resolved, dose delay/reductions based on non-hematologic AEs are applicable. If treatment has to be delayed for AEs, then no escalation is possible.		

Non-Hematologic AE (except alopecia, lymphopenia, nausea, vomiting, weight gain and DVT/PE)					
On L	Day 1 of Each Cycle (within the prior 72 hours)				
Grade Delay					
2-4	Delay up to 4 weeks until all resolved (to grade \leq 1). If unresolved after 4 weeks, then stop. If resolved, dose delay/reductions based on ANC and platelets are applicable. If treatment has to be delayed for AE, then no escalation is possible.				

In case of thrombocytopenia or anemia in Arm 3 (vorinostat + cRA + TMZ), TMZ will be dose-reduced first, and then vorinostat on an alternating basis for each time a dose reduction becomes necessary.

A minimum of 4 weeks of treatment shall be required for a patient to be considered as having received an adequate trial to evaluate efficacy. All patients will be considered evaluable for toxicity and will be followed for at least 30 days after completion of treatment.

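### No stated blood-count criterion governs the day-15 temozolomide course in Arms 2 and 3, and the required mid-cycle count may be drawn after that course has begun

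*Combined protocol and SAP*

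**What the plan says.** **Schedule.** For Arm 3, Section 5.1.3 states "Temozolomide will be administered orally on days 1-7 and 15-21". For Arm 2, Section 5.1.2 adopts "150 mg/m2/day of temozolomide on days 1-7 and days 15-21". Only the days matter here; the dose level is not at issue.

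**Temozolomide rules (5.4.2.3).** The section opens with "Dosing is based on adverse events (AEs) during the prior treatment cycle". The delay paragraph begins "On day 1 of each cycle (within the prior 72 hours), ANC" and goes on to the count thresholds. The matching table is headed "Hematologic AE on Day 1 of Each Cycle (within the prior 72 hours before Day 1"). The hematologic reduction table uses the worst counts of the previous cycle, and its strongest action is a reduction of one dose level.

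**Start of a new cycle (5.4.1).** Neutrophil and platelet recovery is required before the next cycle begins. A general clause lets all three drugs carry on in later cycles while toxicity remains acceptable.

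**Partner drugs (5.4.2.1 and 5.4.2.2).** For vorinostat: "For grade 3 or greater toxicities, treatment will be withheld and the patients will be monitored until toxicities resolve to" below grade 2. The isotretinoin section has the same sentence.

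**Attribution and order (5.4.2).** Dose reductions follow the agent responsible for the toxicity. For thrombocytopenia or anemia in Arm 3, "temozolomide will be dose-reduced first, and then vorinostat on an alternating basis".

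**Monitoring.** The note to the hematologic table in 5.4.2.3 says "A complete blood count must be performed on days 14 and 28", within 72 hours either way, counted after the first daily dose of the cycle. Section 7.1 requires weekly counts in cycle 1 and then, if no significant toxicity is seen, counts every two weeks, each with a 3-day tolerance. It also allows laboratory tests whenever clinically indicated.

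**The concern.** The delay and reduction rules for counts work once per cycle, but temozolomide is started twice per cycle. The second start has no stated count criterion, while the partner-drug sections contain a hold that acts within the cycle. The one mid-cycle count that every cycle requires is also allowed to fall after the second start.

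Cytopenia is foreseeable here. Section 3.3.8.1 lists thrombocytopenia and leukopenia as known temozolomide events. Section 3.2.7 reports vorinostat-related thrombocytopenia in 69 of 305 patients (22.6%), and grade 3-5 in 34 of 305 (11.1%). Section 2.6 says that dose-dense temozolomide has not yet been studied with vorinostat.

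Patient safety is at stake first. Consistency of exposure comes second: if investigators fill the gap differently, the dose-limiting toxicities that drive Arm 3 dose-finding (5.1.3.1, 5.1.3.2) and the Phase II one-third toxicity rule (9.1, 11.2) will be observed under differing practice.

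**Working it through.** The plan gives no figure to reproduce. The check is a comparison of the sections, followed by day-window arithmetic.

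**Step 1. Does any temozolomide count rule reach day 15?**
- Delay for neutrophils or platelets (5.4.2.3): day 1 of a cycle.
- Reduction for neutrophils or platelets (5.4.2.3): worst values of the previous cycle; no hold.
- Count recovery (5.4.1): start of a new cycle.
- Stop for a grade 4 event (5.4.2.3): not expressly tied to day 1, but limited to non-hematologic events.

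None sets a count criterion for day 15. The second course is 7 of the 14 scheduled temozolomide doses in a cycle.

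**Step 2. Do the partner-drug holds cover cytopenia within the cycle?**
- The hold sentence in 5.4.2.1 and 5.4.2.2 does not exclude hematologic toxicity. Both sections add a minimum two-week rest for non-hematologic toxicity only, which implies that the general hold is wider.
- Each section deals with later cycles in a separate paragraph, so the hold reads as acting when the toxicity occurs.
- The hold sentence has no attribution limit, but 5.4.2 ties reductions to the causative agent. Thrombocytopenia is a listed vorinostat toxicity. Whether isotretinoin would be held for a cytopenia attributed to temozolomide is open.

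The contrast is therefore clearest in Arm 3. In Arm 2 the only partner is isotretinoin, where the hold is uncertain.

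**Step 3. When may the mid-cycle count be drawn?** Window = nominal day ± 3 days; restart = day 15.

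| Reading of day 14 | Window | Permitted days on or after day 15 | Second-course doses due before the latest draw day | Doses due through that day |
|---|---|---|---|---|
| Cycle day 14 | 14 − 3 = 11 to 14 + 3 = 17 | 15, 16, 17: 3 of 7 | 2 (days 15-16) | 3 (days 15-17) |
| 14 days after the first dose, i.e. cycle day 15 | 15 − 3 = 12 to 15 + 3 = 18 | 15, 16, 17, 18: 4 of 7 | 3 (days 15-17) | 4 (days 15-18) |

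**Step 4. How old can the previous count be?** The day-1 check may use a count up to 3 days old. Day 17 is 16 days after day 1 and day 18 is 17 days after it. From cycle 2 on, the interval between required counts can therefore reach 3 + 16 = 19 or 3 + 17 = 20 days, spanning the restart.

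**Step 5. Does cycle 1 differ?** The first weekly count falls on days 4-10 (day 7 ± 3) or days 5-11 (day 8 ± 3), before the restart. No temozolomide rule in 5.4.2.3 uses it within the cycle.

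**The case against.** The other side has several good points.

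- **Continuation is conditional.** The general clause in 5.4.1 names all three drugs and makes continuation depend on acceptable toxicity. A reader might infer that the plan requires temozolomide to go ahead on day 15 whatever the count. It does not: it is silent, and a physician may hold the drug by judgement. But the clause gives no count, and 8.9 defines unacceptable toxicity by what happens after a set number of dose reductions, so it does not fill the gap.
- **Not every temozolomide rule is bound to day 1.** The grade 4 non-hematologic stop is not, so the point must be confined to cytopenia.
- **The reduction order in 5.4.2 is not contradicted.** A reader might see a clash between reducing temozolomide first and holding vorinostat first. The order concerns reductions, not holds: vorinostat could be held now and temozolomide reduced next cycle.
- **Monitoring is more frequent than the day-14 note suggests.** Cycle 1 counts are weekly, the move to two-weekly counts is conditional, and extra tests are allowed. This may yield an earlier count, but attaches no temozolomide action to it.
- **More dose-limiting toxicities are not shown.** Under 5.3.1 a hematologic DLT generally needs grade 4, and afebrile grade 4 neutropenia counts only if it fails to recover to grade 1 or below within 7 days. Further dosing of a patient who already has a DLT adds no new DLT patient.
- **Differences between sites and an effect on an Arm 2 MTD are unsupported.** Section 2.11 describes a single-institution trial, and 5.1.2 gives Arm 2 no Phase I component for temozolomide. Variation between investigators, and an effect on Arm 3 dose-finding, remain possible.

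**Conclusion.** The point holds for cytopenia. The plan states no count criterion for the day-15 temozolomide course in Arms 2 and 3, and the required mid-cycle count can come after that course starts. Followed as written, the plan permits temozolomide to restart during a severe cytopenia for which vorinostat is withheld. This is more than missing detail, because the three drug sections treat the same mid-cycle event differently.

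Size: 3 of the 7 permitted draw days (days 11-17), or 4 of 7 (days 12-18), fall on or after the restart, with up to 3 or 4 doses taken by the day of the draw. These fractions describe the width of the window; they are not probabilities. Nor are the 7 of 14 scheduled doses a count of affected patients. Only patients with a mid-cycle severe cytopenia are concerned, and the documents give no rate for that. The effect on DLT counts, on Arm 3 dose-finding and on the Phase II toxicity rule is possible but cannot be quantified.

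Assumptions: the partner-drug hold covers hematologic toxicity and acts within the cycle, as the structure of 5.4.2.1 and 5.4.2.2 implies; and the grade 3 boundary lies near the reduction thresholds in 5.4.2.3 (neutrophils below 1 and platelets below 50 × 10⁹/L), since the grading appendix is not in the supplied text. The window arithmetic depends on neither.

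**What to change.** Reconcile Sections 5.4.1, 5.4.2, 5.4.2.1, 5.4.2.2, 5.4.2.3 and 7.1 on two matters:

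1. State how hematologic toxicity seen in mid-cycle applies to the day-15 temozolomide course, consistently with the vorinostat and isotretinoin sections and with the attribution principle in 5.4.2. The same edit should settle whether isotretinoin is held for a cytopenia attributed to temozolomide.
2. Reconcile the mid-cycle count window in 5.4.2.3 and 7.1 with the day-15 restart, so that the count already required is available when that course begins. Say whether day 14 means cycle day 14 or 14 days after the first dose.

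The clinical team decides the rule, its trigger and its scope; none is proposed here. The cost is protocol wording and less scheduling freedom for the mid-cycle draw. No additional test is needed.
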